### 3. Study Objective and Specific Aims

Specific Aim 1: To determine the feasibility of using ICG fluorescence through the Asimov Imaging Platform for axillary reverse mapping by comparing lymphatic visualization using blue dye (standard of care) versus ICG fluorescence imaging.

Specific Aim 2: To define optimal image acquisition parameters of using ICG fluorescence through the Asimov Imaging Platform for axillary reverse mapping to inform the clinical workflow.

- 2a. To define dynamic range of ICG fluorescence signal in lymphatic vessels and background.
- 2b. To assess image contrast as a function of ICG dose and time post-injection.

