##### Research Procedures:

ARM mapping with ICG fluorescence using the Asimov Platform: The research procedures will include using ICG fluorescence for the ARM mapping. OnLume will provide a sterile drape designed specifically for the OnLume Asimov. 25 mg of ICG and 10 mg Sterile Water will be dispensed for injection by UW Health pharmacy. Before the image acquisition of each patient, ICG will be reconstituted under sterile conditions with Sterile Water for Injection(2.5 mg/1 ml). Shake the vial gently to dissolve. Reconstituted ICG must be used within 6 hours after reconstitution. The total dose of dye will be kept below 2 mg/kg of patient body weight.

ICG dosing described in the literature has varied significantly (Table 1). A total dose of 1 ml (2.5 mg) of ICG will be injected subdermally, in divided doses. 0.5 ml will be injected in the subcutaneous fat in the volar surface of the upper arm at the bicipital sulcus and 0.5 ml in the 2nd interdigital space. The two injection protocol follows the published experience by Abacci, et al. with the goal to improve ICG's circulation through the lymphatic vessels. The upper arm injection will be performed within 1 cm of the isosulfan blue dye injection and will occur after induction of anesthesia. At least two minutes of massage will be performed to promote upper limb lymph flow. Visualization of the lymphatics using the Asimov Platform will be attempted

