#### 4.5. Data Collection

Operative data related to ARM: For each case, we will also assess whether blue dye identified lymphatics were visualized (yes/no) in the nodal basin and whether the blue lymphatic was spared (yes/no). We will also assess whether ICG identified lymphatics were visualized (yes/no) in the nodal basin and whether the ICG lymphatics were spared (yes/no). Surgical decision making will be guided by the blue dye only and the ICG fluorescence will not be considered. However, we will still document whether or not the ICG fluorescent lymphatics were spared. We will assess whether intact lymphatic channels were present at the completion of the axillary surgery via both techniques (yes/no/not assessable). We will record time at start of case, any fluorescent imaging, and completion of axillary surgery (defined as removal of last lymph node).

Chart review demographics and tumor characteristics: We will record other limited demographics about the patient including: Age, race/ethnicity, BMI, type of axillary surgery, type of breast surgery, receipt of neoadjuvant systemic therapy, prior axillary surgery, prior receipt of radiation, clinical and pathologic cancer stage (tumor size and lymph node status), and receptor status (estrogen receptor, progesterone receptor, her2neu). We will record the number of lymph nodes removed. We will indicate whether removed lymph nodes had radiotracer, blue dye, or fluorescence. For patients undergoing SLN biopsy, this will allow us to assess whether the SLN is the same as the ARM identified node. We will evaluate for any additional axillary surgeries or complications related to axillary surgery (infection, lymphedema) until 1 year post-surgery. We will document receipt of post-operative radiation.

Technical data related to ICG fluorescence imaging: Beginning at the time of ICG injection, image and video capture of white light reflectance and fluorescence will be collected. Following the operation, post-processing will be conducted to elucidate injection technique superiority. Physicians will confirm software-assisted lymphatic labels in the video and measure vessel diameters.

We will use quantitative fluorescence to define optimal image acquisition parameters. In order to elucidate injection technique superiority, the critical image acquisition parameters that provide surgeons detectable contrast (CNR) of post-injection time, and fluorescence signal retention of lymphatic vessels will be measured.

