#### **4.6. Analysis Plan:**

1. Aim 1: To determine the feasibility of using ICG fluorescence for axillary reverse mapping through the Asimov Imaging Platform by comparing lymphatic visualization using blue dye (standard of care) versus ICG fluorescence imaging: Given the increased optical penetration with the ICG lymphatics, we anticipate greater visualization with the ICG. The proportion of cases where blue dye visualized lymphatics can be seen after 5 minutes post-injection will be reported along with the corresponding 95% confidence interval, which will be constructed using the Wilson score method. The same proportion will be reported for the ICG lymphatics. Comparisons between visualization of lymphatics by blue dye versus ICG fluorescence imaging will be made using test of two proportions. We will also compare whether lymphatics were able to be spared and whether intact lymphatic channels were able to be confirmed via both techniques. We will also generate descriptive statistics of patient characteristics associated with visualization of lymphatics with each approach to explore clinical scenarios when an approach may be less effective. For comparisons, the blue dye is considered the standard of care comparison.
2. Aim 2: To define optimal image acquisition parameters of using ICG fluorescence through the Asimov Imaging Platform for axillary reverse mapping.  
Aim 2a. To define dynamic range of ICG fluorescence signal in lymphatic vessels and background: Imaging acquisition parameters generated from image snapshots and videos will be summarized using standard descriptive statistics, including means, standard deviations, medians and interquartile ranges to characterize the dynamic range of ICG fluorescence signal in lymphatic vessels and the background. Nonlinear regression analyses will be conducted to statistically model CNR as a function of ICG dose and time.  
Aim 2b. To assess image contrast as a function of ICG dose and time post injection: Image contrast (CNR) will be measured for these lymphatics vessels and a time-curve will be developed that demonstrate the change in contrast over time. The magnitude of fluorescence signal retention of ICG in the lymphatic vessels, which is a function of both pharmacokinetics/pharmacodynamics of ICG and the sensitivity of the imaging platform, will be measured. Detectable contrast is defined by the Rose criterion: CNR>3.

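### Aim 2b and the CNR regression include ICG dose, and the text promises a superior injection technique, but every patient receives one dose and one technique

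*Combined protocol and SAP*

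**What the plan says.** Section 3 gives Aim 2b as "To assess image contrast as a function of ICG dose and time post-injection". Section 4.6 repeats that aim and, in the paragraph on Aim 2a, commits to an analysis: "Nonlinear regression analyses will be conducted to statistically model CNR as a function of ICG dose and time".

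Section 4.5 (Data Collection), under the technical imaging data, states: "Following the operation, post-processing will be conducted to elucidate injection technique superiority". The same purpose is repeated later in that section and in Section 4.1, where it is tied to CNR and to how long the fluorescence signal is retained.

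Section 4.5 (Study procedures, Research Procedures) describes what patients receive: "A total dose of 1 ml (2.5 mg) of ICG will be injected subdermally, in divided doses". Of that volume, 0.5 ml goes into the upper arm "at the bicipital sulcus and 0.5 ml in the 2nd interdigital space". The concentration is fixed at 2.5 mg/ml. On technique, "The two injection protocol follows the published experience" of one cited group. There is also an upper limit: "The total dose of dye will be kept below 2 mg/kg of patient body weight".

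No section describes dose cohorts, allocation to different doses or a second ICG injection technique. The range of doses and sites in Table 1 comes from published studies, not from arms of this trial.

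**The concern.** A regression can estimate the effect of a variable only if that variable takes more than one value in the data. A claim of superiority needs at least two things to compare. On the procedures as written, neither ICG dose nor ICG injection technique varies between patients.

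Aim 2 is intended to inform clinical workflow. Faced with this plan, the analyst has three options, none of them specified in advance:

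- drop the dose term;
- report a model that cannot be fitted as described;
- replace dose with dose per kg and present an association with body size as a dose effect.

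The superiority wording also invites a conclusion that no comparator would support.

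**Working it through.** **The plan's own figure.** Section 4.7 gives one precision statement, for the Aim 1 visualization proportion with about 25 patients: standard error below 12% and a 95% interval no wider than 40%.

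- Worst-case SE = √(0.25/25) = 10.0%.
- Wald width = 2 × 1.96 × 0.10 = 39.2%.
- Largest Wilson width at n = 25 = 36.5%.

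The statement reproduces. It does not bear on Aim 2, for which no precision figure is given.

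**Inputs on dose and technique (Research Procedures).** Total ICG is 1 ml × 2.5 mg/ml = 2.5 mg for everyone. Each site receives 0.5 ml × 2.5 mg/ml = 1.25 mg. Total dose, dose per site and set of sites each have one level.

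**Does the cap create variation?** The limit in mg is 2 × weight in kg. It equals 2.5 mg at 2.5/2 = 1.25 kg. At an assumed 45 kg it is 90 mg, and at an assumed 130 kg it is 260 mg. It never alters the dose.

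**Linear model.** Take CNR = b0 + b1·dose + b2·t + b3·t² + b4·dose·t, with dose = 2.5 throughout. It collapses to (b0 + 2.5·b1) + (b2 + 2.5·b4)·t + b3·t². Only three combinations of the five coefficients can be estimated: dose is aliased with the intercept, and dose × time with time. A numerical check with 25 patients and an assumed grid of seven imaging times (5 to 60 minutes) gave 5 columns and rank 3. The aliasing of dose does not depend on that grid.

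**Nonlinear model.** The plan does not give the form. As an illustration, take CNR = A·dose^g·(e^(−k1·t) − e^(−k2·t)). With dose = 2.5, only the product A·2.5^g enters. A = 3 with g = 0.7 gives 3 × 2.5^0.7 = 5.70; A = 5.70 with g = 0 gives the same curve. A steep dose effect and no dose effect therefore fit identically. The Jacobian has 4 parameters and rank 3.

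**Technique.** An indicator equal to 1 for every patient duplicates the intercept: intercept, technique and time give 3 columns and rank 2.

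**Dose per kg.** For an assumed weight range of 50 to 120 kg, 2.5/50 = 0.050 and 2.5/120 = 0.021 mg/kg. For 45 to 130 kg the range is 0.056 to 0.019. In both cases the variable is exactly 2.5 × (1/weight), so it has correlation 1 with 1/weight and carries no information beyond weight.

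**What remains.** Intercept, time and time² give 3 columns and rank 3. The CNR time-curve can be estimated.

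**The case against.** The strongest reply is that little depends on the dose term. This is a feasibility study without a power calculation, ICG findings do not guide surgery, and no decision rule uses a dose coefficient. The detailed text for Aim 2b in Section 4.6 is a contrast time-curve, signal retention and the CNR threshold of 3, none of which needs dose to vary. A constant regressor simply fails to estimate, and that failure is visible. This stands as a limit on the consequences: Aim 1, the time-curve and the Aim 2a descriptive summaries are unaffected. It does not remove the contradiction, because dose is named in a numbered aim and in the committed regression.

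A second reply is that the plan never defines dose per kg, and that the data list includes BMI but not weight. That is correct; the body-size confounding is conditional on someone making that substitution. The protocol's remark about deeper lymphatics in obese patients (Section 2) also concerns blue dye. That body size affects ICG contrast is a plausible inference, not something the protocol states.

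A third reply is that technique might mean blue dye versus ICG, since Section 4.6 elsewhere uses the word for those two. This reading does not fit: the superiority wording sits under ICG imaging data and is tied to CNR and fluorescence retention, which blue dye does not provide. Nor is it rescued by the two ICG sites. Both are injected in every patient, no comparison between sites is planned, and no method is given for attributing axillary signal to one of them. It is true that Section 4.6 contains no formal superiority test, so here the fault is an unsupported stated purpose, not a failed planned test.

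**Conclusion.** The concern holds. There is one dose level and one ICG injection technique, so the information on either effect is zero at any sample size, and enrolling more patients would not help. One of the two predictors named in Aim 2b, and the whole of the technique-superiority purpose, cannot be addressed by the design. The time component can.

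The result for dose and technique rests only on the procedures being followed as written. The weight ranges, the imaging-time grid and the nonlinear form are illustrative assumptions and do not affect it.

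**What to change.** Sections 3, 4.1, 4.5 (Data Collection) and 4.6 must be reconciled with the Research Procedures. The repair that needs only wording is:

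- In Sections 3 and 4.6, state Aim 2b and the regression as CNR against time after injection, at the single dose the protocol already specifies. Remove dose as a model term.
- State that no dose-response conclusion will be drawn.
- Delete the technique-superiority wording in Section 4.1 and in both places in Section 4.5 (Data Collection).
- If body size is of interest, enter BMI, which is already collected, as a named covariate and report it as such.

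This adds no patients, procedures or data collection. The cost is a narrower stated aim. If the investigators want to keep the dose or technique question, the design would have to contain the variation that the analysis needs; whether and how to do that is a clinical decision on which this review takes no position.

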**Figure 1. Axillary reverse mapping (ARM).**

(A) Sentinel lymph nodes and typical lymphatic drainage patterns from the breast are identified (green). Lymphography with (B) blue dye is challenging due to the non-specific binding to the lymphatics (blue) and poor signal retention. (C) Lymphatic vessels are shown clearly with ICG lymphography (white). Although ICG easily highlights large lymphatic vessels, small and critical lymphatic vessels, which can be as small as 1 mm in diameter, are unable to be seen. *The clinical need in spatial and sensitivity resolution highlights the need for improved FGS imaging systems.*

Fluorescence-guided surgery (FGS) with indocyanine green (ICG) represents an opportunity to greatly enhance the potential of the ARM procedure to increase the surgeon's confidence in identifying the lymphatic architecture before focusing on the operative field. As ICG has shown to offer deeper optical penetration than blue dye with ability to detect lymphatic channels located up to 2 cm deep, surgeons can follow the route of drainage from the injection site through lymphatic vessels to preserve its patency.

In this proposal, we will use the Asimov Imaging Platform for fluorescence-guided surgery in the operating room. The Asimov can be used without altering external (i.e., room) light functionality or levels. This will enable real-time visualization of lymphatics to support ARM and would represent a significance advancement.

Technical gaps in the literature limit our understanding of ICG fluorescence for ARM that impact implementation of this approach within the clinical workflow. Specifically, we need to quantify the critical image acquisition parameters that provide 1) surgeons' detection contrast (CNR) of post-injection time and 2) fluorescence signal retention of lymphatic vessels. The post-injection time is valuable for elucidating the optimal clinical workflow. Although some studies inject more than two hours before surgery, others inject immediately before the axillary surgery. In healthy patients, ICG typically reaches the nearest draining lymph node within 15 minutes, but because lymphatic clearance and backflow are dependent on the damage to vasculature, the optimal post-injection imaging time point will vary depending on the severity of damage to lymphatic vasculature. Thus, the clinical workflow is difficult to establish and optimize.

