#### **4.7. Sample Size:**

We will plan to enroll approximately 0-20 patients undergoing SLN biopsy and 0-15 patients undergoing an ALND for a total of about 25 patients. The proposed total sample size is sufficient to generate descriptive statistics with an adequate level of precision. Specifically, the proportion of cases where lymphatics can be seen after 5 minutes post-injection will be estimated with a standard error of less than 12% and the corresponding 95% confidence interval will be no wider than 40%.

No power calculation is calculated for this feasibility study.

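### The Aim 2 regression of CNR on dose and time has no patient or vessel term and no stated unit of analysis, although its data are repeated images and vessels from about 25 patients

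*Combined protocol and SAP*

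**What the plan says.** Section 4.6 gives the modelling plan for Aim 2 in one sentence: "Nonlinear regression analyses will be conducted to statistically model CNR as a function of ICG dose and time". Dose and time are the only terms named.

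The data for that model are repeated within patients:

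- Section 4.6, Aim 2a: "Imaging acquisition parameters generated from image snapshots and videos will be summarized using standard descriptive statistics".
- Section 4.6, Aim 2b: "Image contrast (CNR) will be measured for these lymphatics vessels and a time-curve will be developed". Vessels are in the plural, and detectable contrast is defined as CNR above 3.
- Section 4.5, Data Collection: "Beginning at the time of ICG injection, image and video capture of white light reflectance and fluorescence will be collected". No end of imaging is fixed. Times are logged case by case for the start of the operation, for fluorescence imaging and for the end of the axillary surgery.

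Section 4.7 sets enrolment at "0-20 patients undergoing SLN biopsy and 0-15 patients undergoing an ALND for a total of about 25 patients". Section 2, in the text after Figure 1, expects patients to differ: "the optimal post-injection imaging time point will vary depending on the severity of damage to lymphatic vasculature". Section 4.5, Study procedures, gives every patient the same total of 2.5 mg ICG, divided between two sites.

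For Aim 1, section 4.6 names both the unit (the case) and the interval method (Wilson). For the CNR model it names neither.

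**The concern.** Images are nested in vessels and vessels in patients, and only the patients are independent. A regression with no term above the single image counts each image as separate information and returns one curve for everyone. Three things are at stake.

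1. Any standard error or interval attached to the curve, or to the time at which it crosses CNR 3, would reflect the number of images and not the roughly 25 patients.
2. The spread between patients in arrival and fading of signal would not be estimated. Aim 2 is meant to inform the clinical workflow. A single curve says when average contrast passes 3, not in what share of patients it has done so.
3. With no common imaging window, late times come only from patients still being imaged, and patients with more labelled vessels or frames carry more weight.

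Dose cannot absorb differences between patients. With one total dose for all, the named model is in practice a curve in time alone.

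**Working it through.** **The plan's own figure.** The only precision statement (section 4.7) is for the Aim 1 visualisation proportion: standard error below 12%, 95% interval no wider than 40%. At n = 25 the largest standard error is sqrt(0.25/25) = 10.0%, and the widest Wilson interval is 36.5% (Wald 39.2%). The figure reproduces. It counts patients and says nothing about the CNR model, for which no precision is stated.

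**Inputs.** From the documents: about 25 patients, repeated images, more than one vessel possible, no fixed end of imaging. Not in the documents, and therefore assumed: observations per patient (m), within-patient correlation (ICC), curve shape, variances and imaging length.

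**Step 1: design effect.** True SE / pooled SE = sqrt(1 + (m − 1) × ICC), for ICC 0.05 to 0.5:

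- m = 2: sqrt(1.05) to sqrt(1.5) = 1.02 to 1.22
- m = 5: sqrt(1.2) to sqrt(3) = 1.10 to 1.73
- m = 20: sqrt(1.95) to sqrt(10.5) = 1.40 to 3.24
- m = 100: sqrt(5.95) to sqrt(50.5) = 2.44 to 7.11

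This formula is for a mean under equal correlation, so it is only a rough guide for a curve.

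**Step 2: simulation of the curve.** 25 patients with two vessels each; CNR = A(exp(−ke·t) − exp(−ka·t)) with median A = 8, ka = 0.15 and ke = 0.01 per minute; vessel log-SD 0.2 on amplitude; independent residual SD 1; imaging length uniform on 30 to 120 minutes; 200 runs per scenario. Between-patient log-SD was 0.1 to 0.5 on amplitude and 0.1 to 0.3 on the rates. The target was fitted CNR at 60 minutes. Coverage is measured around the average estimate, so it isolates the standard-error problem.

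| Frames per vessel | Observations per patient | True SE / pooled SE | Coverage of pooled 95% interval |
|---|---|---|---|
| 1 per 10 min | about 16 (394/25) | 1.8 to 3.0 | 46 to 70% |
| 1 per 5 min | about 30 (757/25) to 31 (771/25) | 2.6 to 4.3 | 31 to 58% |
| 1 per min | about 149 (3728/25) to 150 (3743/25) | 6.0 to 9.4 | 15 to 28% |

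Patient-clustered standard errors gave 91 to 96% coverage in the same scenarios. With no variation between patients or vessels (one frame per 5 minutes) the ratio was 1.05 and pooled coverage about 95%. The problem is therefore the ignored clustering, not the curve shape.

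**Step 3: late times.** A separate simulation used one frame per minute and lognormal imaging length with median 60 minutes and log-SD 0.4. The share of patients imaged past 80 minutes is P(Z > ln(80/60)/0.4) = P(Z > 0.72) = 0.24, or about 6 of 25. The five patients with most late frames supplied about 95% of frames at or after 80 minutes. The ratio of the pooled curve to the true mean at 100 minutes was 0.995 when imaging length was unrelated to amplitude, 1.245 at a correlation of 0.3 and 1.432 at 0.6.

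**Step 4: dose.** The total is 1 ml × 2.5 mg/ml = 2.5 mg for every patient. A dose coefficient has no planned variation behind it; only incidental variation, such as dose per kilogram, remains.

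**The case against.** The strongest reply is that the plan is silent rather than wrong. A reader might infer that it prescribes an ordinary pooled fit with every frame treated as independent. It does not: section 4.6 never says ordinary, pooled or independent. A nonlinear mixed model is also nonlinear regression, and the plural wording is compatible with one fit per patient. This stands, so the defect is an omission that permits the pooled fit.

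Second, section 4.6 promises no standard error, interval or test for the CNR curve, so understated uncertainty harms only what is later reported. This also stands. It does not touch the missing between-patient spread or the selective late data, which affect the curve and its crossing of CNR 3 directly.

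Third, the size cannot be derived from the documents. That is correct: with a few snapshots per patient the understatement is less than twofold.

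Fourth, a reader might infer that the late curve will be biased. That needs a link between imaging length and signal, and the documents report none. They do not even say that imaging stops when the operation ends. The cohort mixes sentinel node biopsy with axillary dissection, which makes a link conceivable but does not show one.

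Finally, this is one aim of a feasibility study with no power calculation, and a heavily parameterised mixed model may not fit with about 25 patients. That argues for a simple model or a two-stage analysis, not for leaving the method unstated.

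**Conclusion.** The point holds as an omission that should be corrected before analysis. As named, the model has no patient or vessel term, the plan sets no unit of analysis or common imaging window, and a fit with those terms alone could not describe the differences in timing that the protocol itself expects.

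If frames were pooled, reported standard errors would be too small by a factor of about 1.0 to 1.7 with 2 to 5 observations per patient (ICC 0.05 to 0.5), and roughly 2 to 9 with sampled video. Both ranges rest on assumed frame rates, correlations and variances. A claim that uncertainty will be understated several-fold is not supported without those assumptions.

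Late times would depend on few patients whatever the link between imaging length and signal. Imprecision there is to be expected; bias is only a possibility.

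**What to change.** Amend the Aim 2 text in section 4.6 to make the patient the unit of inference, by one of two routes:

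- a nonlinear mixed-effects model of CNR over time with patient random effects and vessel within patient, kept as simple as about 25 patients can support; or
- a curve fitted to each patient, from which time to CNR above 3, time of peak and retained signal are derived and summarised across patients. Patients who never reach CNR 3 are counted as not reached, or censored at their last image, and are not dropped.

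Under either route, state the frame-sampling rule in advance, use patient-level or patient-clustered intervals, report the spread between patients, and show the number of patients contributing at each time. The Aim 2a descriptive summaries should name the same unit.

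The dose term in section 4.6 and the single total dose in section 4.5, Study procedures, must be reconciled, so that the plan says what dose effect, if any, the data can estimate.

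The cost is a few sentences of analysis plan and modest analyst time, with no new data. Intervals will be wider, and the late part of the curve will be visibly less certain.
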